10.1. Risk / Benefit Assessment

Potential Risks: Subjects in the GOS and hGOS groups will consume 7.5-15g/day of the prebiotics or placebo preparations as a drink. Possible side effects of the GOS and hGOS groups may include mild to moderate bloating, gas (flatulence), belching, abdominal pain or discomfort, and vomiting. Individuals will be withdrawn from the study if treatment leads to severe side effects.

Potential Benefits: Substances defined as "prebiotics" (a substrate that is selectively utilized by host microorganisms conferring a health benefit per the latest definition of the International Scientific Association for Probiotics and Prebiotics, ISAPP) have a demonstrated beneficial effect in humans and animals. Galacto-oligosaccharides (GOS) in particular have been shown to alleviate symptoms of lactose intolerance and other minor gastrointestinal manifestations in adequate doses.

A compromised gut barrier, dysbiosis and inflammation are hallmarks of the aging gut with consequences that can range from mild GI manifestations like constipation, abdominal pain, and flatulence, to disorders of the gut-brain axis and other conditions not directly associated with the GI tract. This study will add to the knowledge of beneficial modulation of the microbiota to mediate restoration of the gut barrier and biomarkers of inflammation. A positive outcome from

this study will further advance research to improve nutritional conditions and overall health of older individuals in long-term care.

10.2. Assessment of Safety

Participants will be withdrawn if during the first 10 days of study participation, they experience a 2 level change in one or more of the most reported side effects (bloating, flatulence, watery stools, abdominal pain as assessed by questions 2 (abdominal pain), 6 (abdominal discomfort), 8 (constipation), 16 (diarrhea), 22 (abdominal distention), 26 (abdominal bloating), 31 (nausea), or 33 (vomiting) on the PROMIS Gastrointestinal Symptom Scale as compared to their baseline responses. Participants who have surpassed 10 days of study participation and experience a 2 level change in one or more of the most reported side effects (as described above) as compared to baseline, they will be asked to reduce the dose of study product to one sachet of 7.5 mg per day. The study product can be taken all at once or distributed between two time points. If the PROMIS Gastrointestinal Symptom Scale does not improve upon reducing the dose, the participant will be withdrawn from the study. If 5 or more of the first 20 subjects enrolled experience a 2 level change in the most commonly reported side effects (bloating, flatulence, watery stools, abdominal pain) compared to baseline or higher adverse event leading to subject discontinuation, we will stop the study temporarily and request the medical monitor to do an unblinded assessment of the data. The medical monitor (unblinded) will assess subjects who discontinued due to the specified adverse effects to determine if they are all in one arm of the study or range across arms. The medical monitor will assess if there is a safety signal in a specific arm or treatment dose over the other that warrants the closure of the study. Since the medical monitor will be the person determining continuation or discontinuation of the study, the study team will remain blinded and unbiased.

Participants who choose to withdraw from the study will be followed up (via text or email communication) to determine safety and efficacy outcomes. Reasons for discontinuation will be documented in the study RedCap database.

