6.7. Withdrawal / Discontinuation of Enrolled Participants

At baseline and every week after for the duration of the study, participant will answer a 33 question gastrointestinal symptom assessment with the PROMIS Gastrointestinal Symptom Scale (Spiegel, et al, Am J Gastrol, 2014). If a subject experience and increase in 2 levels over baseline in their response to questions 2 (abdominal pain), 6 (abdominal discomfort), 8 (constipation), 16 (diarrhea), 22 (abdominal distention), 26 (abdominal bloating), 31 (nausea), or 33 (vomiting) on the PROMIS Gastrointestinal Symptom Scale, they will be a) withdrawn from the study if the participant is in the first 10 days of their participation, or b) asked to go back to the lower dose of 5g sachets twice daily and reassessed in 3 days, if the participant has passed day 10 of participation. If participants are able to tolerate the lower dose, they will continue participating in the trial albeit consuming the lower dose of the prebiotic treatment. Likewise, if a participant develops a condition that is an exclusion criterion or participant noncompliance increases risk of decreased study integrity, the participant will be withdrawn from the study.

If 5 of the first 20 subjects enrolled experience a change of 2 levels on questions 2, 6, 8, 16, 22, 26, 31, 33 on the PROMIS Gastrointestinal Symptom Scale (bloating, flatulence, watery stools, abdominal pain) compared to baseline or higher adverse event leading to subject discontinuation, we will stop the study temporarily and request the medical monitor to do an unblinded assessment of the data. The medical monitor (unblinded) will assess subjects who discontinued due to the specified adverse effects to determine if they are all in one arm of the study or range across arms. The medical monitor will assess if there is a safety signal in a specific arm or treatment dose over the other that warrants the closure of the study. Since the medical monitor will be the person determining continuation or discontinuation of the study, the study team will remain blinded and unbiased.

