9.2. Aim-Specific Plans

Plans for Aim 1 (A1): Validate 15 g/day dose safety and tolerability (absence of GI adverse effects) of GOS and hGOS in healthy adults.

Method. We will report descriptive statistics for demographics, basic medical history, prescription and over the counter, and dietary supplements, including means and standard deviations for continuous variables, and percentages and ranges for categorical data. We will report the number and percent of all individuals (intent to treat) who had any adverse event (prompted or in response to an open-ended question). We will also report the number and percent of events over time, as well as the severity of the event.

Statistical analysis for A1. Data will be presented as mean \pm SD for variables that are normally distributed, or median (IQR) for variables not normally distributed. Binary/categorical outcomes will be reported as a percentage with confidence interval.

Plans for Aim 2: Establish a biological signature of GOS and hGOS through assessment of prebiotics effects vs placebo on:

(A2.1) Abundance of beneficial gut bacteria and restoration of the gut microbiome saccharolytic potential

Method. Determination of abundance of beneficial bacteria (*Bifidobacterium* and *Akkermansia* species) in the gut microbiome of treatment and placebo groups and the microbiome saccharolytic potential by Whole Genome Shotgun (WGS) sequencing⁵⁵. For assignment of saccharolytic (SAC) and non-saccharolytic (NON_SAC) phenotypes we will use the reference study by Vieira-Silva *et al.*²⁶ as described⁹.

Statistical analysis (A2.1). we will perform both exploratory analysis and statistical testing for changes in plasma cytokines. Data will be presented as mean \pm SD. To find the change of microbiome abundance under difference circumstance, Mann-Whitney-Wilcoxon matched pair tests between baseline and 4 weeks follow-up will be performed for abundance of beneficial gut bacteria in each treatment arm. To compare the change of microbiome abundance in three arms, we will apply the Kruskal-Wallis test whether the change of microbiome abundance is the same among three groups. Due to multiple testing was proposed in A2.1, p values will be corrected for the total number of comparisons with a controlled false-discovery rate (FDR)

ditching statistical significance: Looking beyond a much used and abused measure would make science harder, but better. *Nature* 567, 283-283.

(A2.2) Modulation of biomarkers of inflammation

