9.3. Planned Interim Analyses (If Applicable)

We will review safety data (adverse events) continuously, however, no formal interim analyses are planned.

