10.4. Safety Monitoring

Investigators will assess subjects at each visit and over the phone or via text (or email) each week of the study at days 0, 7±2, 14±2, 21±2, and 28±2 as well as day 7±2 post-intervention. If AEs as defined in this protocol are identified (a 2 level change in one or more of the symptoms as compared to baseline as assessed by questions 2 (abdominal pain), 6 (abdominal discomfort), 8 (constipation), 16 (diarrhea), 22 (abdominal distention), 26 (abdominal bloating), 31 (nausea), or 33 (vomiting) on the PROMIS

Gastrointestinal Symptom Scale). The treatment will be first be reduced to one 7.5g sachet per day (taken either at once or divided between two time periods if the participant has been participating for \geq 10 days. The treatment will be discontinued if the participant is in the first 10 days of participation, and the AE will be recorded. Also, participants who report severe side effects (interfering significantly with subject's usual function) will be withdrawn from the study immediately. If 5 or more of the first 20 subjects enrolled experience a 2 level change in the most reported side effects (bloating, flatulence, watery stools, abdominal pain as assessed by questions 2 (abdominal pain), 6 (abdominal discomfort), 8 (constipation), 16 (diarrhea), 22 (abdominal distention), 26 (abdominal bloating), 31 (nausea), or 33 (vomiting) on the PROMIS Gastrointestinal Symptom Scale compared to baseline or higher adverse event leading to subject discontinuation, we will stop the study temporarily and request the medical monitor to do an unblinded assessment of the data.

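### The one arm comparison defined for the unblinded safety review covers only participants who discontinued, so it is weighted toward the 10 g/day phase and reflects intolerance at 15 g/day only in part

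*Combined protocol and SAP*

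**What the plan says.** Once the 5-of-20 trigger is met, sections 6.7 and 10.2 pause the study and ask the medical monitor to look at the unblinded data. Two steps follow, in the same words in both sections. The first compares arms among "subjects who discontinued due to the specified adverse effects to determine if they are all in one arm of the study or range across arms". Step two reads "The medical monitor will assess if there is a safety signal in a specific arm or treatment dose over the other" and goes on to the closure decision, without saying which participants are counted. Section 10.4 repeats the trigger and gives no arm comparison.

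The event that drives all this is "a 2 level change in one or more of the symptoms as compared to baseline", on eight listed PROMIS items. Its handling depends on when it occurs. In the first 10 days the participant is withdrawn. After day 10 the dose is reduced first; in 6.7 the participant is "asked to go back to the lower dose of 5g sachets twice daily and reassessed in 3 days". Those who tolerate the lower dose stay: "they will continue participating in the trial albeit consuming the lower dose of the prebiotic treatment". Section 10.2 withdraws those who do not improve, and 10.4 withdraws anyone with severe side effects. Symptoms are assessed "each week of the study at days 0, 7±2, 14±2, 21±2, and 28±2", and once more a week after the intervention.

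For final reporting, 9.2 states: "We will report the number and percent of all individuals (intent to treat) who had any adverse event". Section 9.3 states: "We will review safety data (adverse events) continuously, however, no formal interim analyses are planned".

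**The concern.** Whether a participant discontinues depends on the dose phase as well as on tolerance. The same 2-level change puts a participant into the defined comparison if it is reported in the 10 g/day phase, but may leave that participant out if it is reported at 15 g/day. Section 4.4 names 15 g/day as the dose the trial sets out to confirm, so the comparison is thinnest where the question lies.

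The review decides whether the study closes. A monitor who relied on the defined subset could see discontinuations spread across arms while dose-reduced participants clustered in one arm. The continuous safety review in 9.3 is not described as being by arm, so it does not clearly fill the gap.

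**Working it through.** The plan gives no error rate or event rate for the 5-of-20 rule, so there is no figure to reproduce. The check is mainly a comparison of the sections.

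**Step 1. Who enters the defined comparison** (sections 4.1, 6.7, 7.6, 10.2, 10.4)

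| 2-level change reported | Scheduled dose | Handling | In the defined comparison? |
|---|---|---|---|
| Days 1–10 | 10 g/day | Withdrawn | Yes |
| After day 10, tolerates reduced dose | 15 g/day | Stays in | No |
| After day 10, no improvement | 15 g/day | Withdrawn after reduction | Yes, later |
| Either phase, severe | Either | Withdrawn | Yes |
| First reported at final visit, not severe | 15 g/day | None specified; treatment is ending | Not named |

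**Step 2. Timing of contacts.** The on-treatment contacts fall on days 5–9 (7±2), 12–16 (14±2), 19–23 (21±2) and 26–30 (28±2). Only the first lies within days 1–10. Reports at the second and third go to dose reduction first. At the fourth there is little or no dosing left to stop. A change that begins on days 8–10 may first be reported at the second contact and be handled by reduction. The comparison is therefore weighted toward the 10 g/day phase but is not a complete record of it.

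**Step 3. How small the subset could be.** Take 5 qualifying participants and let each have discontinued independently with probability f. The documents give no f, so the values below are assumed.

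- Expected number in the comparison = 5f.
- P(at most one) = (1−f)^5 + 5f(1−f)^4.

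| f | Expected number | P(at most one) |
|---|---|---|
| 0.25 | 1.25 | 0.63 |
| 0.50 | 2.5 | 0.19 |
| 0.75 | 3.75 | 0.02 |

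With one participant or none, asking whether all are in one arm tells the monitor nothing. With k participants, equal allocation and no arm effect, the chance that all fall in one arm is (1/3)^(k−1): 0.33 for k = 2 and 0.012 for k = 5.

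**Step 4. Illustration with assumed events.** Suppose one GOS and one placebo participant are withdrawn at day 7, and three hGOS participants are reduced at day 14 and improve. In the order GOS/hGOS/placebo:

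- Defined comparison: 1/0/1.
- All qualifying participants: (1+0)/(0+3)/(1+0) = 1/3/1, a total of 5.

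If any 2-level change counts toward the trigger, these five meet it. The 1/3/1 split is not itself strong evidence. With 5 events, equal allocation and no arm effect, P(hGOS holds at least 3) = (40+10+1)/243 = 51/243 = 21%, and P(some arm holds at least 3) = 3 × 51/243 = 153/243 = 63%. The example shows that the monitor would see a different picture. It does not show that a closure decision would change.

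**The case against.** The strongest reply is that adjacent text already covers the gap. The monitor is asked to assess the data, not only the discontinuations. The sentence after the comparison carries the closure decision and asks about arm or dose with no restriction to those who left. A comparison by dose naturally reaches participants at 15 g/day. Section 11.7 also has the medical monitor review adverse event reports, and 10.4 treats a 2-level change as an adverse event, so the monitor will know of these participants. All of this stands. A reader might infer that the protocol excludes dose-reduced participants from any arm comparison; it does not. What remains is that the only comparison with a stated population and criterion omits them, and the broader assessment has neither.

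The trigger's grammar is also ambiguous. The phrase about leading to discontinuation may qualify only the higher adverse event, or the whole condition. On the second reading the trigger and the comparison cover the same people, the mismatch between them disappears, and the illustration would not cause a pause. Dose-reduced participants who stay in would then be absent from both. The documents do not settle which reading is meant.

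Finally, one might argue from the 3-day reassessment in 6.7 that a change first reported at the final visit could never lead to discontinuation. That goes too far. The 3-day interval appears only in 6.7, and leftover packets are collected at the final visit (7.6), so dosing after it is doubtful. The sound statement is that the plan does not place these participants in the comparison.

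**Conclusion.** The point holds in a limited form. In 6.7 and 10.2 the only arm comparison with a defined population and criterion is among participants who discontinued. Because handling changes at day 10, that population is weighted toward the 10 g/day phase and reflects intolerance at 15 g/day only through failed reductions and severe cases. Including the others is permitted but left to the monitor.

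The consequence is confined to the pause and closure review. A reader might infer that the primary outcome or the Aim 1 report loses these participants. The documents do not support that, because 9.2 reports all individuals with any adverse event.

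No frequency can be given: the documents state no event rate, discontinuation share or reduction-failure rate. The shares in step 3 and the events in step 4 are assumptions. This is an inexpensive improvement to a safety review, not a demonstrated failure of it.

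**What to change.** In 6.7 and 10.2, replace the restriction to discontinued participants with every participant who has a qualifying 2-level change or a higher adverse event, whether withdrawn, dose-reduced or first reported at the final visit. Have these tabulated by arm and by dose at onset, with the number at risk in each cell. Participants withdrawn in days 1–10 never reach 15 g/day and should not be in that denominator.

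The cost is one sentence in each section, one short table if the pause is triggered, and slightly more work for the monitor. The symptom data are already collected weekly and the monitor is already unblinded for this review. The sample size, visit schedule and participant handling rules stay as they are.

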10.3. Unanticipated Problems, Adverse Events, Serious Adverse Events

Unanticipated Problems: An unanticipated problem is any incident, experience or outcome that meets all three OHRP criteria (1) unexpected (in severity, specificity, frequency, or nature), (2) related or possibly related to the research, and (3) suggests the research places subjects or others at greater risk than previously known or recognized.

Adverse Event (AE) Definitions: An AE is “any untoward medical occurrence associated with the use of a drug in humans, whether or not considered drug related.” For the purposes of this definition, “untoward” means unfavorable, negative, or harmful. An AE is any event observed or reported that is associated with the intervention, without regard to causality.

Serious Adverse Events (SAE) Definition: An AE or suspected adverse reaction will be considered “serious” if, in the view of either the Investigator or Sponsor, it results in any of the following outcomes:

- Death;
- Is life-threatening (immediate risk of death);

- Requires inpatient hospitalization or prolongation of existing hospitalization;
- Results in persistent or significant incapacity or substantial disruption of the ability to conduct normal life functions;
- Results in congenital anomaly/birth defect;
- Is an important medical event that may require an intervention to prevent one of the outcomes listed above.

Grading the Severity of Adverse Events and Events of ‘Special Interest’:

The severity or intensity of an AE describes the degree of impact upon the subject and/or the need for, and the extent of medical care required to treat the AE. The Investigator will use the adjectives MILD, MODERATE, or SEVERE to describe the maximum intensity of the AE. For purposes of consistency, these intensity grades are defined as follows:

MILD	Does not interfere with subject’s usual function.
MODERATE	Interferes to some extent with subject’s usual function.
SEVERE	Interferes significantly with subject’s usual function.

Relatedness Definition:

The Investigator will assess relatedness for all AEs (serious and non-serious). Factors considered when assessing the relationship of an event to the investigational product:

- (1) Alternative etiology – Is the event due to the underlying disorder being studied or to another known disorder?
- (2) Known relationship – Has the event been observed before in patients treated with this investigational product or similar products?
- (3) Temporal relationship – Is there a reasonable temporal relationship between the time of onset of the event and the administration of the investigational product?
- (4) Concomitant medication – Is the event a known side effect of a concomitant medication?

Based on the previous factors we will consider the following descriptions when assessing relationship of an event to the investigational product:

Definite: There is a reasonable causal relationship between the investigational product and the AE, when the event responds to withdrawal of the investigational product (de-challenge) and recurs with re-challenge by administration of the investigational product.

Probable: There is a reasonable causal relationship between the investigational product and the AE. The event responds to de-challenge. Re-challenge not required.

Possible: There is a reasonable causal relationship between the investigational product and the AE. De-challenge is lacking or unclear.

Not Likely: There is a temporal relationship between the investigational product administration and the AE, but there is not a reasonable causal relationship between investigational product and the event.

Unrelated: There is not a temporal or causal relationship to the investigational product administration.

The Investigator will record causal relationship in the source documents, as appropriate, and report such an assessment in accordance with the SAE reporting requirements, if applicable.

Expectedness Definition: An assessment of expectedness will be performed for each AE and SAE. Previously reported expected effects of prebiotic administration include abdominal pain (cramps), bloating, flatulence (gas) and diarrhea (loose stools >3 times/day). During the study, GI side effects will be expected and only AEs that are meet the definition of severe AE or considered an SAE will be reported to the IRB or FDA.

AE and SAE Assessment, Follow-up Procedures: The Investigator will record all directly observed AEs and all AEs spontaneously reported by the study subject beginning from the time the subject begins use of the investigational product through 7 days after the last dose of the investigational product. Changes in health status after the subject has provided informed consent but before the subject begins use of the investigational product shall be recorded as changes in the medical history.

The Investigator will assess subjects at each visit for the occurrence of AEs. In order to avoid bias in eliciting AEs, subjects should be asked the following non-leading question: "Have there been any changes in your health since your last visit?"

All AEs (serious and non-serious) reported by the subject must be recorded regardless of if a causal relationship with the investigational product is suspected. Each AE will be assessed to determine if it meets the criteria for a serious adverse event (SAE). If an SAE occurs, expedited reporting will follow local and international regulations as appropriate.

Reporting and Documentation Procedures: AE and SAE reporting periods will extend from the signature of the informed consent through the End of the Study Visit or until 7 days after the last dose of the investigational product. If an SAE occurs, [name] will be notified within 24 hours of awareness of the event by the Investigator. This timeframe also applies to adding new information (follow-up) on previously forwarded SAE reports. In the rare event that the Investigator does not become aware of the occurrence of an SAE immediately, the Investigator will report the event within 24 hours of first awareness of the SAE and document the time of his/her first awareness of the SAE. For all SAEs, the Investigator will pursue and provide information to the Sponsor or designee in accordance with the timeframes for reporting specified above. This will generally include a description of the AE in sufficient detail to allow for a complete medical assessment of the case and independent determination of possible causality. Information on other possible causes of the event, such as concomitant medications and illnesses must be provided. All observed or volunteered AEs regardless of treatment group or suspected causal relationship to the investigational product(s) will be reported.

Participant Notification of New Information:

Participant will be notified via email, text message and/or phone call.

